## **2.2. Study Objectives**

Primary:

- *To estimate the relative BA of ritlecitinib (PF-06651600) pediatric capsules (3 x 10 mg capsule, Test) relative to adult 30 mg capsule (Reference) under fasted conditions in healthy adult participants.*
- *To estimate the relative BA of ritlecitinib (PF-06651600) administered as 30 mg spray congealed beads (Test) relative to adult 30 mg capsule (Reference) under fasted conditions in healthy adult participants.*

Secondary:

- *To evaluate the safety and tolerability of 10 mg capsules, 30 mg capsules and spray congealed beads at the 30 mg dose of ritlecitinib (PF-06651600) administered to healthy adult participants under fasted conditions.*

Other:

- *To characterize the PK of ritlecitinib (PF-06651600) administered as pediatric capsules (3 x 10 mg capsule), adult 30 mg capsule and 30 mg spray congealed beads in healthy adult participants under fasted conditions.*
- *To assess the sensory characteristics and overall palatability of spray congealed beads by healthy participants.*

### **3. INTERIM ANALYSES, FINAL ANALYSES AND UNBLINDING**

No formal interim analysis will be conducted for this study. As this is an open-label study, the sponsor may conduct unblinded reviews of the data during the course of the study for the purpose of safety assessment.

### **4. HYPOTHESES AND DECISION RULES**

#### **4.1. Statistical Hypotheses**

No hypotheses are required.

#### **4.2. Statistical Decision Rules**

No decision rules are required.

### **5. ANALYSIS SETS**

#### **5.1. Pharmacokinetic (PK) Analysis Set**

##### **5.1.1. Concentration Analysis Set**

*The PK concentration population is defined as all participants randomized and treated who have at least 1 concentration in at least 1 treatment period.*

##### **5.1.2. Parameter Analysis Set**

*The PK parameter analysis population is defined as all participants randomized and treated who have at least 1 of the PK parameters of primary interest in at least 1 treatment period.*

#### **5.2. Pharmacodynamic Analysis Set**

None.

#### **5.3. Safety Analysis Set**

*All participants assigned to study intervention and who take at least 1 dose of study intervention. Participants will be analyzed according to the product they actually received.*

#### **5.4. Other Analysis Sets**

None.

## **5.5. Treatment Misallocations**

All analyses will be performed on an “as-treated” basis and will not include data from participants who are randomized but not treated.

If a participant takes a treatment that is not consistent with the treatment they are assigned to, for example takes a treatment out of sequence or takes the same treatment twice, then they will be reported under the treatment that they actually receive for all safety and PK analyses, where applicable.

## **5.6. Protocol Deviations**

Participants who experience events that may affect their PK profile (eg, lack of compliance with dosing) may be excluded from the PK analysis. At the discretion of the pharmacokineticist a concentration value may also be excluded if the deviation in sampling time is of sufficient concern or if the concentration is anomalous for any other reason.

A full list of protocol deviations will be compiled and reviewed to identify major and minor deviations prior to database closure.

### **5.6.1. Deviations Assessed Prior to Randomization**

At Screening, the investigator will assess participants against the inclusion and exclusion criteria as set out in Sections 5.1 and 5.2 of the protocol.

### **5.6.2. Deviations Assessed Post-Randomization**

A full list of protocol deviations for the study report will be compiled prior to database closure. Any significant deviation from the protocol will be reviewed prior to database closure and a decision taken regarding evaluation for each analysis population.

## **6. ENDPOINTS AND COVARIATES**

### **6.1. Efficacy Endpoint(s)**

None.

### **6.2. Safety Endpoints**

Any events occurring following start of treatment or increasing in severity will be counted as treatment emergent.

Events that occur in a non-treatment period (for example, Washout or Follow-up) will be counted as treatment emergent and attributed to the previous treatment taken.

The following data are considered in standard safety summaries (see protocol for collection days and list of parameters):

- *adverse events*,

- *laboratory data.*

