1.3. Schedule of Activities

The SoA table provides an overview of the protocol visits and procedures. Refer to the **STUDY ASSESSMENTS AND PROCEDURES** section of the protocol for detailed information on each procedure and assessment required for compliance with the protocol.

The investigator may schedule visits (unplanned visits) in addition to those listed in the SoA table, in order to conduct evaluations or assessments required to protect the well-being of the participant.

Visit Identifier Abbreviations used in this table may be found in Appendix 10	Screening ^a	Treatment Period								Follow-up ^b	Early Termination/ Discontinuation
		Period 1		Period 2		Period 3					
Days Relative to Day 1	Day -28 to Day -2	Day -1	Day 1	Day 2	Day 1	Day 2	Day 1	Day 2	Telephone Contact		
Study Day	-28 to -2	-1	1	2	3	4	5	6	33 to 40		
Informed consent	X										
CRU confinement		X	→	→	→	→	→	X			
Inclusion/exclusion criteria	X	X ^c									
Demographic information ^d	X										
Medical/medication, drug, tobacco and alcohol history (update) ^e	X	X ^c									
Complete/limited physical examination ^f	X	X						X		X	
Safety laboratory ^g	X	X						X		X	
Pregnancy test (WOCBP only)	X	X						X		X	
Contraception check ^h	X	X						X	X	X	
FSH (post-menopausal women only)	X										
Urine drug testing	X	X									
12-Lead ECG ⁱ	X		X ^o					X		X	
Blood pressure and pulse rate, temperature ^j	X		X ^o					X		X	
HIV, HCVAb, HBsAg, HbcAb ^k	X										

Visit Identifier Abbreviations used in this table may be found in Appendix 10	Screening ^a	Treatment Period								Follow-up ^b	Early Termination/ Discontinuation
		Period 1		Period 2		Period 3					
Days Relative to Day 1	Day -28 to Day -2	Day -1	Day 1	Day 2	Day 1	Day 2	Day 1	Day 2	Telephone Contact		
Study Day	-28 to -2	-1	1	2	3	4	5	6	33 to 40		
TB screening (QuantiFERON® Gold Test)	X										
Lipid panel ^g	X										
Study intervention administration ^l			X		X ^p		X ^p				
Taste assessment							X ^q				
Pharmacokinetic blood sampling ^m			X	X	X	X	X	X			
Pfizer Prep D1 Banked Genetic Biospecimens ⁿ			X ^o								
Prior/concomitant treatments	X	X	X						X	X	X
CRU discharge									X		
Serious and nonserious adverse event monitoring	X	X	→	→	→	→	→	X	X	X	

- a. Participants will be screened within 28 days of the first dose of study intervention.
- b. Follow-up contact will occur by telephone and must occur at least 28 to 35 days after the last administration of ritlecitinib (PF-06651600).
- c. Update since screening, if applicable.

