- d. Including measurement of height and weight at screening.
- e. Include history of alcohol abuse, tobacco/nicotine containing products, licit and illicit drug use or dependence within 6 months of Screening. For Day -1, records would be reviewed or updated only.
- f. Complete (full) physical examination must either be conducted at Screening or upon Admission of Period 1 (Day -1) only; limited physical examination is required upon discharge/early termination/discontinuation; brief (limited) physical examination may be performed as appropriate at other times at the investigator's discretion if there are findings during the previous examination, new/open adverse events.
- g. Safety laboratory testing must be collected within 28 days prior to first administration of study medication (see [Section 8.2.4](#)). Safety laboratory assessments including urinalysis, hematology, and chemistry will be performed following at least 4 hours fasting; however, the lipid profile requires fasted conditions for at least 10 hours. Samples will be collected prior to discharge or if the reason for discontinuation is related to an AE. Additional laboratory assessments may be required to evaluate potential case of Hy's Law or adverse event as deemed necessary by the investigator. Refer to [Table 4](#) in [Section 10.2](#).
- h. The contraception check is an opportunity to confirm that contraception, if assigned, is used consistently and correctly.
- i. Single ECG will be used.
- j. Single BP will be collected in the supine position.
- k. For hepatitis B, all participants will undergo testing at screening for hepatitis B surface antigen (HBsAg) and hepatitis B core antibody (HBcAb); If HBsAg is negative and HBcAb is positive, HBsAb should be evaluated.
- l. Participants assigned to receive study intervention under fasted conditions must be fasted for at least 10 hours pre-dosing and 4 hours post-dosing.

PFIZER CONFIDENTIAL

Visit Identifier Abbreviations used in this table may be found in Appendix 10	Screening ^a	Treatment Period										Follow-up ^b	Early Termination/ Discontinuation
		Period 1			Period 2		Period 3						
Days Relative to Day 1	Day -28 to Day -2	Day -1	Day 1	Day 2	Day 1	Day 2	Day 1	Day 2	Telephone Contact				
Study Day	-28 to -2	-1	1	2	3	4	5	6	33 to 40				

- m. PK dosing will be captured on the day of dosing at the following timepoints: pre-dose and at 0.25, 0.5, 1, 1.5, 2, 3, 4, 6, 9, 12, 16 and 24 hours post-dose.

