- n. If not collected on the designated collection day, collect at the next available time point when biospecimens are being collected in conjunction with a participant visit.
- o. Collected at pre-dose.
- p. Dosing of each period to be separated by at least a 48-hour washout interval. The participants will be discharged on Day 2 of Period 3.
- q. Review taste assessment questionnaire and instructions with participants prior to dosing in Period 3, Day 1. Each participant will record the sensory attributes at timed intervals of 0 (immediately after dosing), 5, 10 and 20 minutes after administration using a taste assessment questionnaire (see [Appendix 9](#)).

Table 1. Pharmacokinetic Sampling Schema for Period 1, Period 2 and Period 3

Visit Identifier	Period 1, Period 2 and Period 3												2
	1												
Study Day	0 ^a	0.25	0.5	1	1.5	2	3	4	6	9	12	16	24
Hours Before/After Dose	X												
Study Intervention Administration	X												
Ritlecitinib (PF-06651600) PK blood sampling ^b	X	X	X	X	X	X	X	X	X	X	X	X	X

a. Predose PK samples. Any time prior to dosing ritlecitinib (PF-06651600) on the day of dosing.

b. Ritlecitinib (PF-06651600) PK blood samples (2 mL blood to yield approximately 0.5 mL plasma) are to be collected.

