4. STUDY DESIGN

4.1. Overall Design

The study will be conducted as a Phase 1, open-label, single dose, randomized, 3 period, cross-over design in a single cohort of approximately 12 healthy male or female participants at a single center. Participants will be randomized into 2 sequences of treatment as described in [Table 2](#):

Sequence 1 (n=6): A B C

Sequence 2 (n=6): B A C

Table 2. Study Design and Treatments

Treatment Sequence	Period 1	Washout	Period 2	Washout	Period 3
1 (n=6)	A	At least 2 days of washout between dosing	B	At least 2 days of washout between dosing	C
2 (n=6)	B		A		C

n = number of participants.

Treatment A: ritlecitinib (PF-06651600) 30 mg intact adult capsule

Treatment B: ritlecitinib (PF-06651600) 3 × 10 mg pediatric capsules

Treatment C: ritlecitinib (PF-06651600) 30 mg spray congealed beads

Since ritlecitinib (PF-06651600) is rapidly eliminated ($t_{1/2} \sim 2$ hours), there will be at least a 48-hour washout between each dose.

Blood samples for PK analysis will be collected pre-dose and at 0.25, 0.5, 1, 1.5, 2, 3, 4, 6, 9, 12, 16 and 24 hours post-dose.

Participants will participate in the study up to approximately 2.5 months, including the screening and follow-up periods. Participants will be screened within 28 days of the first dose of study intervention and if all entry criteria are fulfilled, the participants will report to the CRU on the day prior to Period 1 Day 1 dosing (Day -1). On Day 1 of each period, participants will receive a single dose of study intervention. Capsules and spray congealed beads will be administered with approximately 240 mL of ambient temperature water, and will be swallowed (not chewed). Participants will be fasted for at least 10 hours pre-dosing and 4 hours post-dosing.

For the taste assessment in Period 3, participants will be asked to not verbalize their responses and not discuss taste with other participants until after they have filled out the responses in the questionnaire.

Participants will be confined in the CRU for a total of at least 7 days (6 nights which includes admission to the CRU on Day -1) and discharged at the discretion of the investigator. A follow-up phone call will be made at least 28 calendar days and up to 35 calendar days after the last administration of the study interventions to capture any potential AE and confirm appropriate contraceptive usage.

Participants who withdraw from the study may be replaced at the discretion of the sponsor.

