8.2.1. Physical Examinations

A complete (full) physical examination will be completed only at the Screening visit or upon admission to the clinic (Day -1) and will include, at a minimum, head, ears, eyes, nose, mouth, skin, heart and lung examinations, lymph nodes, and gastrointestinal, musculoskeletal, and neurological systems.

A brief (limited) physical examination is required upon discharge/early termination/discontinuation and will include, at a minimum, assessments of general appearance, the respiratory and cardiovascular systems, and participant-reported symptoms. Brief (limited) physical examination may also be performed as appropriate at other times at the investigator's discretion if there are findings during the previous examination, new/open AEs.

Physical examinations may be conducted by a physician, trained physician's assistant, or nurse practitioner as acceptable according to local regulation.

Height and weight will also be measured and recorded as per the [SoA](#). For measuring weight, a scale with appropriate range and resolution is used and must be placed on a stable, flat surface. Participants must remove shoes, bulky layers of clothing, and jackets so that only light clothing remains. They must also remove the contents of their pockets and remain still during measurement of weight.

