### **8.3.4. Adverse Events**

Adverse events will be reported in accordance with the sponsor reporting standards by treatment.

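### Last-treatment attribution of adverse events gives the beads (always third) 28 to 35 days of attribution time, against about 2 days for each capsule

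*SAP*

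**What the plan says.** SAP 6.2 treats any event after the start of treatment as treatment emergent. For events in a non-treatment period it adds: "for example, Washout or Follow-up) will be counted as treatment emergent and attributed to the previous treatment taken". No lag or maximum window follows. SAP 8.3.4 then states: "Adverse events will be reported in accordance with the sponsor reporting standards by treatment".

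The design fixes the position of the beads. Protocol 4.1 has two sequences, A B C and the one quoted here: "Sequence 2 (n=6): B A C". Treatment C is third in both.

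The timing comes from the Schedule of Activities (Protocol 1.3):

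- Footnote p on spacing: "Dosing of each period to be separated by at least a 48-hour washout interval". The study-day row puts the three doses on Days 1, 3 and 5.
- Footnote p on discharge: "The participants will be discharged on Day 2 of Period 3", which is Study Day 6.
- Footnote b on follow-up: "Follow-up contact will occur by telephone and must occur at least 28 to 35 days after the last administration". The study-day row gives Days 33 to 40.
- Footnote g on safety laboratory samples: "Samples will be collected prior to discharge or if the reason for discontinuation is related to an AE".

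Protocol 8.2.1 adds: "A brief (limited) physical examination is required upon discharge/early termination/discontinuation". Protocol 8.3.1 collects adverse events until at least 28 days after the last dose. The sole secondary objective (Protocol 3) is the safety and tolerability of the three products.

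**The concern.** Attributing late events to the last treatment taken evens out in a crossover where each treatment comes last equally often. Here it cannot. Randomisation only swaps A and B between Periods 1 and 2, so every completer's follow-up time goes to the beads.

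The by-treatment adverse event table would then have columns that differ in two ways:

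- **Length.** The beads column includes four to five weeks of ordinary life after discharge. The capsule columns stop at the next dose.
- **Intensity.** Capsule time is spent wholly in the unit. Bead time is about one day in the unit, then a long stretch covered by one scheduled telephone contact. The single scheduled set of post-dose safety assessments also falls in the beads' window.

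A reader who compares the columns could take background events from follow-up as a feature of the bead formulation. Equally, events missed after discharge could make the beads look better than they are. The primary bioavailability estimates are not at stake.

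**Working it through.** **Inputs.** Doses on Study Days 1, 3 and 5, discharge on Study Day 6 and the call on Study Days 33 to 40 (Protocol 1.3). Twelve participants, all taken as completers (Protocol 4.1). Attribution runs from each dose to the next dose, or from the last dose to the call (SAP 6.2).

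**The plan's own figure.** Last dose on Day 5: 5 + 28 = 33 and 5 + 35 = 40. This reproduces the stated Days 33 to 40.

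**Attribution time per completer.**

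- Period 1 capsule: 3 − 1 = 2 days.
- Period 2 capsule: 5 − 3 = 2 days.
- Beads: 33 − 5 = 28 to 40 − 5 = 35 days.
- Ratio of beads to one capsule: 28/2 = 14 to 35/2 = 17.5.
- Beads' share of the total: 28/(2 + 2 + 28) = 87.5% to 35/(2 + 2 + 35) = 89.7%.
- Each capsule's share: 2/32 = 6.3% down to 2/39 = 5.1%.

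**Twelve completers.**

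| | A | B | C |
|---|---|---|---|
| Attribution, participant-days | 12 × 2 = 24 | 12 × 2 = 24 | 12 × 28 = 336 to 12 × 35 = 420 |
| Of which confined | 24 | 24 | about 12 × 1 = 12 |
| Scheduled post-dose assessment sets | 0 | 0 | 12 |

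After discharge, the beads have 28 − 1 = 27 to 35 − 1 = 34 days per completer.

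**Sensitivity to spacing.** The 48-hour interval is a minimum. With 3 days between doses the ratio is 28/3 = 9.3 to 35/3 = 11.7. With 4 days it is 28/4 = 7 to 35/4 = 8.75.

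**Detection.** For a completer, the only scheduled post-dose laboratory tests, ECG, vital signs and physical examination are on Period 3 Day 2 (Study Day 6). That is about 24 hours after the beads, 72 hours after the Period 2 capsule and 120 hours after the Period 1 capsule. Clinically relevant laboratory changes are recorded as adverse events (Protocol 8.2.4), as are examination findings that meet the definition of an adverse event (Protocol 9.4.2). If such a finding is dated when it is first seen, it goes to the beads whichever product preceded it. The documents do not spell out that dating rule, so this step is an inference.

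**Causality.** Relatedness is judged against the study intervention (Protocol 10.3.3), which Protocol 6 defines as all three products together. It does not assign an event to a formulation.

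**After the proposed split.** On the scheduled days, onset within 48 hours has 12 × 2 = 24 participant-days for each product. Later onset has 0 for A and B, and 12 × (28 − 2) = 312 to 12 × (35 − 2) = 396 for C.

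**The case against.** The case against accepts the day counts and disputes their importance.

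- **Nothing is tested.** The objective is to evaluate safety, with no hypotheses and no decision rules, and last treatment taken is an explicit, reproducible rule. This stands and keeps the point minor. A descriptive by-treatment table still invites comparison of its columns, and nothing in either document warns the reader.
- **The sponsor reporting standards are not in the documents.** They may contain onset columns or footnotes. That cannot be excluded, but SAP 6.2 as written sets no limit.
- **Relatedness assessment considers timing.** It can help separate background events weeks after a single dose of a drug with a half-life of about 2 hours. This stands in part: it helps with a related-events table, but does not correct a table of all events.
- **The detection argument is partly inference.** SAP 6.2 refers to events that occur in a period, and the protocol allows unscheduled laboratory tests, extra vital signs and limited examinations. Those extra assessments are not systematic. The imbalance comes from the protocol schedule, and the SAP can only disclose it.
- **A 48-hour split equalises calendar time only.** This stands. The beads' hours 24 to 48 fall after discharge, and the Period 3 Day 2 assessments remain in the beads' early window. A 24-hour cut would lie wholly within confinement for all three products, but would halve the early window. Neither cut is a stated risk window.
- **Infection is a named risk and may appear late.** The split therefore has to keep and show later events.

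**Conclusion.** The point holds, as a minor one. For completers on the scheduled days, the stated rule gives the beads 14 to 17.5 times the attribution time of either capsule, and 7 to 8.75 times even if doses were 4 days apart. Confined time is about half that of a capsule, and every completer's scheduled post-dose assessment set falls in the beads' window.

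The day counts are firm. Their effect on recorded adverse events is not known and could go either way, so no event-level figure is claimed. The result assumes that all 12 participants complete, that discharge is on Period 3 Day 2 and that the unseen sponsor standards add no cut-off. In a participant who stops early, the long follow-up would instead go to the last product taken. The PK analyses are untouched.

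**What to change.** Keep the last-treatment attribution in SAP 6.2 for the overall listing and table. In SAP 8.3.4, split the by-treatment adverse event table by time of onset:

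1. From dosing to 48 hours, or to the next dose if that comes sooner.
2. More than 48 hours after dose, still showing the last treatment taken. Do not label this part follow-up: with 3-day spacing, each capsule would have 12 × 1 = 12 confined participant-days in it.

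Base any side-by-side reading of the formulations on part 1 only. Add a footnote stating that:

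- participants had taken all planned earlier products before the beads;
- hours 24 to 48 after the beads fall after discharge;
- the only scheduled post-dose laboratory tests, ECG, vital signs and physical examination are on Period 3 Day 2, so findings first detected there fall to the beads whichever product preceded them.

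State that the 48-hour cut comes from the dose spacing and is not a risk window.

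The cost is SAP wording, one extra table split and a footnote. It needs no new data and no protocol change, and no event is dropped. The Period 3 Day 2 detection imbalance is disclosed, not removed.

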### 6.3. Other Endpoints

#### 6.3.1. PK Endpoints

Blood samples for PK analysis of ritlecitinib (PF-06651600) will be taken according to the Schedule of Activities given in the protocol.

The following PK parameters will be calculated for ritlecitinib (PF-06651600) (if possible) from the concentration-time data using standard noncompartmental methods:

**Table 2. Noncompartmental PK Parameters**

PK Parameter	Analysis Scale	Ritlecitinib (PF-06651600)
AUC inf *	ln	A, D
AUC last	ln	A, D
C max	ln	A, D
T max	R	D
t 1/2 *	R	D
CL/F*	ln	D
Vz/F*	ln	D
T last	R	D

Key: A=analyzed using statistical model, D=displayed with descriptive statistics,  
ln=natural-log transformed, R=raw (untransformed), \*=if data permits.

